We will use evidence- and theory- (cognitive behavior modification) based strategies to optimize participation in both the RET and WLC conditions (61). Multiple strategies will be used as they are more effective than a single strategy approach (62). For RET we will contact by phone anyone who misses a workout to provide social support for continuing their exercise program. We will offer flexible hours and weekends to allow the Veterans choices of the best day and time for their work out. For both the RET and WLC groups, plenty of parking is available and transportation will be reimbursed up to \$750. We will also keep in close contact with our participants and remind them through cards and phone calls of their appointments. We will also distribute small exercise related prizes (t-shirts, exercise balls, etc.) as a way to provide incentive for training session attendance and completion of symptom questionnaires. For those subjects assigned to the resistance exercise condition, we will tally the training session attendance at the end of the first 4 weeks of training and award an incentive to those subjects who attended at least 80% of their scheduled twice-weekly training sessions. For those subjects assigned to the WLC condition, we will tally the completed symptom questionnaires (at least 50% of items have been answered) and award an incentive to those subjects who have completed at least 80% of their weekly symptoms questionnaires. The same procedures will be followed at the second, third and fourth 4 weeks of the 16-week study session. The monetary value for each of these incentive items will be between \$5-10. The incentives will be printed with a promotional logo which will hopefully aid recruitment for the study. The logo will include the lab phone number and email address in order to facilitate current or past subjects sharing lab contact information with prospective participants. Participants will be reimbursed for travel expenses at the standard VA rate up to a maximum reimbursement of \$750. Participants will also receive \$75 for each testing session (\$525 for attending all 7 testing sessions). For those who finish the 16 week trial (RET and WLC) and complete $\geq 80\%$ of scheduled exercise/testing sessions we will award them a \$300 payment towards a gym membership in their local area. In addition, WLC participants who complete $\geq 80\%$ of scheduled testing sessions will be offered 16 weeks of free personal training with our exercise specialists at the VA hospital in Madison and a \$300 payment towards a gym membership in their local area. All Veterans will be informed of these incentives prior to the beginning of the program and periodic reminders will be used as encouragement.

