 - The first day of testing will occur in the MRI simulator room at the Waisman Laboratory for Brain Imaging and Behavior.
 - Psychophysical pain testing will occur during this session, both before and during the MRI simulation procedure.
 - The cognitive task will be introduced and subjects will be permitted to practice the task. This same task will be employed during the MRI simulation as well as actual scans.
- **Physical Activity Assessments**
 - During the week prior to Day 2 participants will wear an activity monitor which will record intensity and frequency of physical activity
- **Participants are assigned to their experimental condition, either RET or WLC**
 - Participants assigned to the RET group will work with study staff to schedule their training sessions for the 16-week trial.
 - Participants assigned to the WLC group will be instructed to maintain their current level of physical activity and exercise for the 16-week trial.

◆ **Day 2 of Testing**

- **Baseline psychophysical, cognitive and functional brain imaging (to occur within 2 months of the first day of testing)**
 - fMRI data collection during psychophysical pain testing and cognitive performance tasks will occur in the 3T MRI room at the Waisman Laboratory for Brain Imaging and Behavior.

◆ **16-Week Trial (will start approximately 1 week after Day 2)**

- **RET group members will attend twice-weekly training sessions (90 minutes) with a personal trainer at the VA Physical Therapy clinic**
- **Outside of test days, WLC group members will go about their typical daily routine**
- **Both groups will complete a small battery of clinical symptom questionnaires on a weekly basis either at home (WLC) or just prior to a training session (RET)**

◆ **Blood Sampling**

- **RET group members will have blood samples drawn one hour before and thirty minutes following their first training session of the week during weeks 2, 7, and 15.**
 - Total volume of blood drawn over the duration of the study for participants in the RET group will be 240 ml.
- **All blood draws will be conducted by a certified phlebotomist who is also a member of the study staff.**
- **Blood draws will take place in the Exercise Psychology Laboratory at the University of Wisconsin-Madison.**

◆ **Days 3, 4 and 5 of Testing**

- **Psychophysical, cognitive and functional brain imaging data will be collected at weeks 6 and 11 of the 16-week trial and one week after completion (week 17)**

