 - fMRI data collection during psychophysical pain testing and cognitive performance tasks will occur in the 3T MRI room at the Waisman Laboratory for Brain Imaging and Behavior.
- **Physical Activity Assessments**
 - During the week prior to Days 3, 4 and 5, participants will wear an activity monitor which will record intensity and frequency of physical activity

◆ **Follow-up Testing**

- ***Psychophysical, cognitive and functional brain imaging data will be collected at 6 and 12 months after completion of 16-week trial***
 - fMRI data collection during psychophysical pain testing and cognitive performance tasks will occur in the 3T MRI room at the Waisman Laboratory for Brain Imaging and Behavior.
- ***Physical Activity Assessments***
 - During the week prior follow-up testing participants will wear an activity monitor which will record intensity and frequency of physical activity

Summary of Experimental Design

This protocol is a randomized controlled trial of RET in GV with CMP. The overall goal of the trial is determine whether RET is an efficacious treatment for GV with CMP. Our primary aims and hypotheses are based on baseline compared to end of treatment responses. However, we have designed our trial to address some of the temporal aspects of the behavioral response by measuring our dependent variables at several points during and following RET and WLC. We feel that this is a critical aspect of the design that will provide valuable data to inform future investigations. Clinical symptoms and brain activity and anatomy will be evaluated throughout the trial to assess changes across time. The WLC group has been employed in order to gauge the impact of resistance training when compared to no treatment in GV with CMP.

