Participants assigned to the exercise condition will be asked to perform resistance training twice per week for 16 weeks. All resistance training bouts will be supervised by trained exercise specialists who possess the necessary education and experience to do so. The minimum requirement to demonstrate possession of the necessary education and experience for this position will be one of the following: certification with a nationally recognized sports medicine agency (for example ACE, ACSM, NSCA), completion of a graduate level course involving clinical exercise testing and prescription, or an advanced degree in exercise science. Exercise training will be conducted in a resistance training facility created specifically for this study at the Madison VA hospital (G2/G4). RET will be conducted on an individual basis to avoid potential mental health benefits accruing from social interaction with group exercise (67). This will help ensure that any detected benefits are specific to the exercise intervention. The exercise specialists will be available throughout the day, including weekends, to allow for flexible workout schedules and increase adherence to the program. If, because of an injury, illness or medical condition unrelated to their study participation, a participant is forced to take an extended layoff, more than 4 weeks, from exercise training, we will offer those individuals the option of restarting the 16-week exercise intervention. If the participant opt to restart the intervention we will also ask them to complete additional, but not more than 3, MRI scans to correspond to their new starting date.

Published methods will be employed to instruct participants on how to perform resistance exercise (68). Great care will be taken to educate participants on how to safely use the exercise equipment. Safety drills will be conducted with each participant at the outset of the training program, and the participants will be monitored during each session. Each participant will be required to practice correct breathing techniques (e.g., avoiding Valsalva). Maximal lifts will never be allowed. Very light loads (e.g. 30% of 4 repetition maximums) will be used

during the first week so participants learn proper breathing and lifting techniques, and habituate to the exercise.

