Power estimates for the trial are based on Specific Aim 1. General multivariate regression models will be used to estimate the time averaged difference in pain ratings and clinical symptom scores (continuous measurements) between the treatment and the control group. With general multivariate regression models we model both the dependence of the response on the explanatory variables as well as the autocorrelation among the responses. In order to achieve 90% power, at alpha equal to .05, with an effect size of .6 (minimum effect size of clinical importance) and with a correlation of .6 between measurements from each individual, the necessary sample size would be 34 subjects per group. If we take into account a 20% subject attrition rate, then the total sample size should be 41 subjects per group. All randomized subjects will be included in the analysis within the appropriate arm that they were randomly assigned (i.e. an intent-to-treat analysis will be used). Noncompliance, protocol deviations, withdrawal or any other problem that occur after randomization will be ignored and the participant's last observed data points will be carried forward in the analyses. Missing data will be assumed to be missing completely at random and appropriate missing data methods will be used (i.e. multiple imputation) to minimize the effect of withdrawal. For the purpose of evaluating Specific Aim 2, a similar methodology will be employed to estimate the time averaged difference in physical activity counts as measured by accelerometry.

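### Cheap improvement, low priority: the weekly symptom form depends on attendance in the exercise arm only, so weekly comparisons could lean toward exercise if pain keeps Veterans from sessions

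*Combined protocol and SAP*

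**What the plan says.** **Collection.** The 16-Week Trial bullet of the Study Schedule has both arms complete "clinical symptom questionnaires on a weekly basis either at home (WLC) or just prior to a training session (RET"). RET has two sessions a week. The bullet does not say which session carries the form, what happens in a week with no session, or which instruments are in the battery.

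**Incentives and contact.** Under Subject Identification and Recruitment, RET is tallied on attendance: the plan will "award an incentive to those subjects who attended at least 80% of their scheduled twice-weekly training sessions". WLC is tallied on forms: it will "award an incentive to those subjects who have completed at least 80% of their weekly symptoms questionnaires". The plan also states: "For RET we will contact by phone anyone who misses a workout to provide social support for continuing their exercise program". That call mentions no symptom score.

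**Layoffs.** The section on the two interventions offers a restart if "a participant is forced to take an extended layoff, more than 4 weeks, from exercise training", but only for an injury, illness or condition unrelated to the study. Shorter absences get no restart, and weekly forms during any layoff are not mentioned.

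**Missing data.** Statistical Considerations says "last observed data points will be carried forward in the analyses", and also: "Missing data will be assumed to be missing completely at random and appropriate missing data methods will be used (i.e. multiple imputation").

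**What the main comparison uses.** Summary of Experimental Design states: "Our primary aims and hypotheses are based on baseline compared to end of treatment responses". Primary and secondary outcomes are retested at lab visits in weeks 6, 11 and 17 in both arms. Statistical Considerations describes a time-averaged model of pain and symptom scores without naming its time points.

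**The concern.** The two collection routes can lose scores for different reasons. A RET Veteran whose flare keeps him from both sessions has, as written, no score that week. A WLC Veteran with the same flare still has a form at home and is rewarded for returning it. The plan's own background section reports that, in earlier fibromyalgia exercise trials, worsening symptoms were believed to reduce adherence and were poorly tracked. If that happens here, the missing RET weeks are the painful ones, and neither carry-forward nor an assumption of missingness completely at random deals with that.

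At stake is the weekly series. It holds the only scheduled symptom scores between baseline and week 6, when training starts and any early exacerbation would show. A score not taken then cannot be recovered later.

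**Working it through.** **Step 1: does the plan's sample size imply weekly scores?** Inputs from Statistical Considerations: 90% power, alpha .05, effect 0.6 SD, correlation .6, 34 per group. Sidedness and number of measurements m are not given.

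n per group = 2 × (z_alpha + z_beta)² × [1 + (m − 1) × .6] / (m × 0.6²)

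- m = 4, one-sided: 2 × (1.645 + 1.282)² × 0.70 / 0.36 = 33.3, which rounds up to the plan's 34. Two-sided: 40.9.
- m = 16: 29.7 one-sided, 36.5 two-sided.

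The 34 fits four measurements, which is also the number of lab assessments from baseline to week 17, better than it fits sixteen weekly ones. This is a hint, not proof.

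**Step 2: model for the weekly series.** The documents give no pain-attendance link, so everything from here is conditional. Assumptions: no true effect; 34 per arm; 16 weekly scores with SD 1 and correlation .6, so the within-person SD is √0.4 = 0.632; likelihood analysis of the available scores. Each RET session is missed with log-odds a + ln(OR) × (that week's deviation from the person's own mean / 0.632), with OR = 1.5, 2 or 3. Per full SD these are OR^(1/0.632) = 1.9, 3.0 and 5.7. The RET week is lost only if both sessions are missed. WLC forms are 20% missing at random, which adds no bias.

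**Step 3: chance of a false RET benefit.** With full data, the standard error of a 16-week average difference is √{2 × [(1 + 15 × .6)/16] / 34} = √(1.25/34) = 0.192. A bias b (negative favours RET) turns the nominal 2.5% into Φ(−1.96 − b/0.192). For b = −0.056 that is Φ(−1.67) = 4.8%. The simulated rates agree.

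| RET sessions missed | RET weeks lost | Bias, SD (OR 1.5; 2; 3) | False benefit |
|---|---|---|---|
| 10% | 1–2% | −0.01 to −0.02 | about 3% |
| 20% | 4–7% | −0.02; −0.03; −0.06 | 3.1%; 3.7%; 4.8% |
| 50% | 26–30% | −0.08; −0.13; −0.20 | 6%; 11%; 18% |

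The 20% row matches the plan's 80% attendance mark. The 50% row is pessimistic. It follows the earlier Gulf Veteran trial (median 6 sessions over 12 weeks), which offered one supervised session a week and fewer supports.

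**Step 4: variations.**
- Form tied to one particular session, 20% missed: −0.05; −0.08; −0.12 SD. The plan says a training session, so either session serving is the more natural reading.
- Weekly pain autocorrelated (AR .5), OR 2 to 3: −0.02 to −0.04 SD at 20% missed, −0.10 to −0.15 SD at 50%.
- Layoff illustration (assumed, no source in the documents): 1 in 10 RET Veterans misses 4 of 16 weeks with pain 1 SD worse. Then 0.10 × 4/16 × 1 = 0.025 SD.

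**Step 5: WLC forms also lost because of pain**, same OR (2; 3):

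| WLC forms lost | Net bias, 20% of RET sessions missed | Net bias, 50% missed |
|---|---|---|
| 5% | −0.012; −0.023 | not run |
| 10% | +0.009; +0.006 | −0.094; −0.136 |
| 20% | +0.050; +0.064 | −0.054; −0.081 |

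At good RET attendance the sign turns once about 10% of WLC forms are lost to pain.

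**Step 6: does the analysis method rescue it?** At 20% missed and OR 3, a likelihood model under missing at random gives −0.054 SD and carry-forward gives −0.054. With AR .5 they give −0.035 and −0.030. Neither removes the bias. Multiple imputation was not simulated; under missing at random it rests on the same assumption.

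**The case against.** The strongest reply is that no stated analysis is shown to use the weekly scores. The primary contrast is baseline to end, the outcomes are retested in the laboratory in both arms, and the false-benefit rates above belong to a 16-week averaged test that the plan never specifies. This stands, and it is why the point is low priority.

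Other parts of the reply also stand:
- The absence of a RET catch-up is inferred from silence in a schedule bullet. Staff may collect the form another way; nothing forbids it.
- Two sessions a week, a gradual start, flexible hours and weekend slots all make a week with no session less likely.
- The background's adherence remark concerns fibromyalgia trials, and the same section reports no adverse events for strength training.
- The direction is not fixed, as Step 5 shows.

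A reader might infer more than the documents support. The Summary of Experimental Design stresses repeated measurement over time, but it does not name the weekly battery, and its mention of measurement after treatment fits the lab visits and follow-ups at least as well. The restart rule might be read as the plan expecting training-related pain to stop attendance; it covers only conditions unrelated to participation.

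What the reply does not answer is that the routes and incentives differ by arm with no written reason, and that aligning them costs almost nothing.

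**Conclusion.** The asymmetry is real and worth removing, as a minor change confined to the weekly series. Weekly comparisons lean toward RET only if pain reduces attendance more than it reduces WLC form completion. On the assumed odds ratios this is about -0.02 to -0.06 SD at 20% of sessions missed with either session serving. That is small beside the 0.6 SD target. It reaches -0.08 to -0.20 SD only at 50% missed, and it can reverse to about +0.05 to +0.06 SD if 20% of WLC forms are lost to pain while RET attendance is good.

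It would be tempting to conclude that the trial's efficacy result is biased toward exercise. The documents do not support that: the baseline-to-end contrast and the week 6, 11 and 17 retests do not depend on this route, and the plan does not say that weekly scores enter the main model.

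**What to change.** 1. **Study Schedule, 16-Week Trial.** Require the weekly battery every week whatever the attendance, including layoffs. Either use a home form on a fixed weekday in both arms, or keep the pre-session form and add a home or phone catch-up for any RET week without a session, using the existing missed-workout call. Give WLC a matching reminder, and record the mode. The catch-up option keeps staffed collection for most RET weeks.
2. **Subject Identification and Recruitment.** Apply the same 80% questionnaire-completion incentive in both arms.
3. **Weekly scores already collected.** Report the number scored by arm and week. Add a two-way shift analysis that makes unscored weeks worse by 0, 0.25, 0.5, 0.75 and 1.0 SD, separately in RET and WLC, and report where the conclusion changes. The shift that would cancel the bias (bias divided by fraction of weeks lost) was 0.17 to 0.98 SD over the cases run, inside that grid. It overcorrects if absences are unrelated to pain, so it is a sensitivity analysis only. Do not present a missing-at-random model as removing this bias.

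**Cost.** One form sent home or one item added to an existing call, a WLC reminder, and a few lines of text. No endpoint, sample size or alpha changes. The downside is less staff oversight of home or phone scores and possible mode differences.

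**What remains.** If pain-related non-response is then equal in both arms (5–20% lost, OR 2 or 3), bias is 0.00 and false benefit 2.3–2.6%. If 10% is lost in each arm with OR 3 in RET and OR 2 in WLC, -0.02 SD and 3.3% remain.

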Musculoskeletal pain in soldiers returned from service in the Persian Gulf War represents an understudied phenomenon that greatly adds to suffering and disability of the men and women who serve our country. These symptoms are difficult to deal with and the lack of knowledge pertaining to pathophysiology has left military physicians poorly equipped to treat symptomatic soldiers (3). Numerous studies have reported musculoskeletal pain as a primary and disabling symptom for GV's. While descriptive data based on self-report are important for highlighting problems, it sheds little light on etiology nor does it suggest treatments. Studies aimed at determining efficacious treatments while testing potential mechanisms of CMP need to be conducted to help treat presently sick Veterans and to help avoid active duty soldiers from entering the downward spiral to disability that accompanies war-related illnesses. Although this research directly tests the influence of RET on pain and physical function, there are numerous health benefits of being active. As detailed in the 2008 physical activity guidelines (<http://www.health.gov/paguidelines/Report/Default.aspx>), regular physical activity is associated with reduced risk for all-cause mortality, coronary heart disease, stroke, hypertension, colon cancer, type 2 diabetes, improved well-being and reduced symptoms of mental health disorders. Therefore, exercise is an important potential treatment with many positive benefits to the Veteran, and few drawbacks.

Specific Aims and Hypotheses

Aim 1: To determine the influence of RET on valid measures of pain (0-100mm visual analogue scale (VAS)), physical function (Physical Component Summary (PCS) of the short-form (SF-36) and patient global impression of change (PGIC) in GV's with CMP compared to WLC. The primary outcome will focus on whether RET results in *clinically meaningful differences*. Secondary outcomes will assess other aspects of pain and mental health of potential importance to the quality of life of GV's including qualitative descriptions of pain, pain coping styles, sleep patterns, self-esteem, symptoms of fatigue, anxiety and depression.

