Hypothesis 1: GV's with CMP assigned to RET will show statistically significant and clinically meaningful improvements in self-reported pain, physical function and PGIC compared to WLC. We also expect significant improvements in the secondary outcomes known to change after exercise training (e.g. sleep, self-esteem, fatigue, anxiety and depression).

Aim2: To determine the influence of RET on total daily physical activity levels using complementary subjective self report and objective measures (accelerometers).

Hypothesis 2: GV's with CMP assigned to RET will show an increase in total physical activity by the end of the trial that is attributable entirely to an increase in RET.

Aim 3: To determine the influence of RET on brain mechanisms of pain **sensitivity** and **regulation** in GV's with CMP compared to WLC. Brain responses to painful heat stimuli will be measured using fMRI. Pain sensitivity will be determined by exposing participants to mild, moderate and strong pain stimuli. Pain regulation will be determined by having the participants perform attention-demanding cognitive tasks while receiving moderately painful stimuli.

Hypothesis 3A (Pain Sensitivity): GV's assigned to RET will show decreased ratings and decreased brain responses to experimental pain stimuli by the end of the treatment trial compared to baseline.

Hypothesis 3B (Pain Regulation): By the end of the treatment trial, GV's assigned to RET will show **decreased** brain responses in areas that process the sensory aspects of pain (e.g. cingulate & sensory cortices), and **increased** brain responses in areas that modulate or inhibit pain when diverting their attention away from a painful stimulus compared to baseline.

Aim 4: To determine the influence of RET on pain-relevant brain white matter tracts in GV's with CMP compared to WLC by conducting DTI analyses of white matter tracts from the thalamus to regions of the brain involved in pain processing and control (e.g. insula, periaqueductal gray, frontal and cingulate regions).

Hypothesis 4A: GV's assigned to RET will show improvements in white matter (measured as increased fractional anisotropy and/or decreased mean diffusivity) compared to baseline.

Research Design and Methods

Pilot subjects:

Five healthy adults (ages 18-60) will be recruited for a single MRI scanning session.

Screening and exclusion criteria for pilot subjects:

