The primary outcome measures to test efficacy are visual analogue scales (VAS) of pain intensity and affect of widespread muscle pain symptoms, the physical component summary (PCS) of the SF-36, and the patient global impression of change (PGIC) scale. These valid measures are widely used and recommended as core outcomes in chronic pain treatment trials (63). The primary outcome measures for Aim 2 are self-report and objectively measured estimates of total physical activity. Self-reported physical activity will be measured using the International Physical Activity Questionnaire (IPAQ). Objective estimates of physical activity will be obtained using an accelerometer during the week immediately preceding the baseline visit to the Waisman brain imaging laboratory, at weeks 5, 10 and 16 of RET or WLC and at 6- and 12-month follow-ups.

Suprathreshold pain sensitivity will be assessed using scaling procedures as described by Gracely and colleagues (64). For painful heat stimuli, subjects will be randomly presented one of three stimuli (45°C, 47°C,

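### Three or four primary efficacy measures are named with no decision rule, so the single alpha of .05 and the 90% power can describe one measure only

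*Combined protocol and SAP*

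**What the plan says.** The two lists of primary measures differ.

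- **Specific Aims and Hypotheses, Aim 1** has three: "valid measures of pain (0-100mm visual analogue scale (VAS)), physical function (Physical Component Summary (PCS) of the short-form (SF-36", and the PGIC. It then turns to the singular, "The primary outcome will focus on whether RET results in", with clinical meaningfulness as the criterion. It neither picks out a measure nor gives a threshold for any of them.
- **Day 1 (Screening Day)** has four if the two pain scales count separately. It opens the list with pain: "The primary outcome measures to test efficacy are visual analogue scales (VAS) of pain intensity and affect of widespread muscle pain symptoms". The SF-36 physical score and the PGIC are then named as the other two.

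Hypothesis 1 is the only wording close to a success criterion. It predicts "statistically significant and clinically meaningful improvements in self-reported pain, physical function and PGIC compared to WLC".

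Statistical Considerations bases power on Aim 1 and gives one calculation: "In order to achieve 90% power, at alpha equal to .05, with an effect size of .6". With a within-person correlation of .6, it arrives at 34 per group. The quantity powered is a time-averaged group difference in pain ratings and clinical symptom scores. The paragraph does not state whether the test is one- or two-sided, how many repeated measurements are averaged, or how the outcomes correlate with one another. The multivariate regression it names is described as handling covariates and autocorrelation, not as a joint test across outcomes.

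**The concern.** The Summary of Experimental Design sets the trial the task of deciding whether RET is efficacious. Suppose PGIC is significant and pain is not. The plan does not say whether efficacy has then been shown, and the rule could be chosen after the data are seen.

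The rule also fixes the trial's operating characteristics. If any one measure suffices, the chance of a false positive exceeds the per-measure level. If all are needed, the chance of success falls below the per-measure power. Only perfectly correlated outcomes would preserve both stated figures.

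**Working it through.** **Inputs from the documents.** Effect size d = .6, within-person correlation ρ = .6, alpha .05, power 90% and 34 per group (Statistical Considerations). Testing at baseline and at weeks 6, 11 and 17 (Baseline Assessment and 16-Week Trial).

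**Assumptions.** m = 4 repeated measurements. A common between-outcome correlation r from 0 to 0.7. Effect .6 on every measure, PGIC continuous, and complete data at 34 per group.

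**1. Reproduce the plan's figure, for one measure.** For a time-averaged difference,

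n per group = 2(z_α + z_β)² × [1 + (m − 1)ρ] / (m d²).

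With m = 4, [1 + 3 × .6]/4 = .70.

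- One-sided: 2 × (1.645 + 1.282)² × .70/.36 = 33.3, so 34. This matches.
- Two-sided: 2 × (1.960 + 1.282)² × .70/.36 = 40.9, so 41.

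Power at 34 per group is Φ(√(34 × .36/(2 × .70)) − z_α) = Φ(2.957 − z_α). That is 90.5% one-sided and 84.1% two-sided. One-sided m = 3 or 5 gives 35 or 33, also close to 34. Two-sided m = 3 or 5 gives 43 or 40. So 34 and 90% fit together for one measure under one-sided testing.

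**2. Any one of k measures suffices.** If independent, the chance of at least one false significant result at two-sided .05 is 1 − .95⁴ = 18.5% for four and 1 − .95³ = 14.3% for three. In the favourable direction only, it is 1 − .975⁴ = 9.6% for four. For correlation r, with c = 1.96 and u standard normal, average over u:

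1 − E{[Φ((c − √r u)/√(1−r)) − Φ((−c − √r u)/√(1−r))]^k},

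dropping the second Φ for the favourable direction only.

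**3. All k measures required.** If independent with 90% each, joint power is .9⁴ = 65.6% for four and .9³ = 72.9% for three. With the two-sided 84.1% for each, it is .841⁴ ≈ 50% for four. For correlation r, joint power is E{[Φ((z_p + √r u)/√(1−r))]^k}, where z_p is the normal quantile of the per-measure power.

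| r | Any of 4, two-sided .05 | Any of 4, favourable only | Any of 3, two-sided .05 | All 4, 90% each | All 3, 90% each | All 4, 84.1% each |
|---|---|---|---|---|---|---|
| 0 | 18.5% | 9.6% | 14.3% | 66% | 73% | 50% |
| 0.3 | 17.4% | 8.7% | 13.6% | 70% | 76% | 57% |
| 0.5 | 15.6% | 7.8% | 12.5% | 74% | 78% | 63% |
| 0.7 | 13.0% | 6.5% | 10.9% | 78% | 81% | 68% |

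**4. A single time point instead of the time average**, two-sided at 34 per group.

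- Week 17 unadjusted: Φ(√(34 × .36/2) − 1.960) = Φ(2.474 − 1.960) ≈ 70%.
- Week 17 adjusted for baseline, variance factor 1 − .6² = .64: Φ(√(34 × .36/(2 × .64)) − 1.960) = Φ(3.092 − 1.960) ≈ 87%.

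**The case against.** The strongest reply is that Hypothesis 1 joins the outcomes with 'and'. If that is the success rule, alpha is safe and only power suffers. This stands as far as it goes: the two readings are not equally supported, and the error inflation arises only under the any-one reading. But Hypothesis 1 states an expectation, not a criterion, and if it were the criterion the 90% would still need restating.

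A second reply is that Hypothesis 1 also asks for clinically meaningful improvement, which would reduce the any-one error. That is true in direction. No threshold is given for any individual measure, so the reduction cannot be sized, and the same threshold would lower power.

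Third, the count of four rests on one section only. Both counts are therefore shown; with three measures the effect is milder but remains.

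A reader might infer three stronger things that the documents do not support.

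- **That the plan tests each measure at .05.** It never says so. The figure appears only as the input to one power calculation.
- **That the .05 and the 90% are false.** They are attainable together for a single measure, as step 1 shows.
- **That 13-19% is the rate of false efficacy claims.** Under two-sided testing it also counts significant worsening, so the favourable-direction figure is the relevant one for that purpose.

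**Conclusion.** The point holds as a gap with numerical consequences. Several measures are called primary, one alpha and one power are given, and no rule connects them.

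Under an any-one rule at two-sided .05, the chance of at least one false significant result is 13-19% for four measures and 11-14% for three. For four measures in the favourable direction alone it is 6.5-9.6%, against 2.5%. Under an all-required rule, alpha holds and joint power is 66-78% for four or 73-81% for three, given 90% on each. If testing is two-sided with four repeated measurements, each measure has about 84% at 34 per group, and joint power for four is about 50-68%.

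The missing rule and the conflict between the lists are plain from the text. The sizes rest on the assumed correlations, the equal effects, the continuous treatment of PGIC and, for the last figure, the assumed sidedness and number of measurements.

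**What to change.** First, reconcile Aim 1 with Day 1 (Screening Day), so that it is clear whether pain counts as one measure or two. Then state one rule before results are seen.

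- **(a) One primary measure.** Name it (pain intensity VAS is one candidate; the choice is the sponsor's). Keep the time-averaged difference that Statistical Considerations powers. Test the remaining measures afterwards in a fixed sequence, each at .05. The cost is that later measures can be claimed only if every earlier one succeeds.
- **(b) All required.** Say so, keep .05 for each, and restate the joint power with the sidedness, the number of repeated measurements and the between-outcome correlation given. The cost is a lower stated power.

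The Summary of Experimental Design bases the primary hypotheses on baseline against end of treatment. If week 17 is therefore chosen as the primary time point, power must be restated for it: two-sided at 34 per group, about 70% unadjusted, or about 87% adjusted for baseline with correlation .6.

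Either rule is a change of wording and adds no participants or visits.
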